10.2 Screening Phase

Screening assessments should be undertaken within 90 days prior to the scheduled PSG titration procedure. Results of standard clinical assessments such as history, physical examination and prior polysomnography testing may be used to identify individuals who may broadly meet trial entry criteria.

Routine clinical evaluations that would be performed as part of the normal clinical care of patients with OSA may be performed prior to informed consent and used as part of the screening assessment; however, no study-related procedures may be performed prior to obtaining full informed consent from the subject. If the subject is subsequently consented and enrolled in the study, the results of standard-of-care tests may be used as study data.

Site personnel will use care in reviewing the subject's clinical status in relation to each inclusion and exclusion criterion and will ensure that appropriately documented results are available prior to concluding that the subject meets trial entry criteria.

Subjects who do not meet the inclusion / exclusion criteria or fail to complete a valid PSG titration study become screen failures and may not be enrolled or participate in any further study procedures.

Once subjects have signed the informed consent document, they must complete screening evaluations within 90 days of the scheduled day of the PSG titration study.

Evaluations will consist of the following:

- Review/ documentation of current medications or agents that may affect sleep or PSG results
- Brief physical examination (Vital signs, Height, Weight, BMI)
- Medical and sleep history

10.3 **PSG Titration Study**

Subjects who meet the inclusion/exclusion criteria will undergo an in-lab PSG titration study to identify the effective therapeutic pressure setting (i.e., AHI < 10/hr.). This PSG titration study will be performed using a commercially-available CPAP mask and hose and will be scored by authorized site personnel.¹

At the conclusion of a valid PSG titration night (i.e., ≥ 4 hours of sleep with no equipment recording failures and results in analyzable data for AHI and ODI values) and identification of a therapeutic pressure setting, the subject will be assessed for proper fit to the FRESCA mask. The subject will breathe on the investigational device set to the titrated pressure for at least a 30-second interval to determine proper FRESCA mask fit.

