10.4 Randomization

Each site will be provided a list of subject numbers to be assigned to subjects as they are evaluated at their screening visit. A screening log will record the subject number, subject initials, date of screening, date informed consent was signed, and whether subject was enrolled. A subject is considered enrolled if they sign the informed consent document, meet all inclusion and exclusion criteria, complete a valid PSG titration study that identifies a therapeutic pressure setting (i.e., AHI < 10/hr.) and have a successful FRESCA mask fit. Each enrolled subject will be randomized to one of two sleep night sequences. Randomization assignments will be computer-generated by the study statistician and obtained through the data management system (EDC). A randomization log will be used to record the assigned randomization sequence.

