11.2 Analysis Populations

The enrolled population will include all subjects who sign the informed consent document, meet all inclusion and exclusion criteria, complete a valid PSG titration study that identifies a therapeutic pressure setting (i.e., AHI < 10/hr). and have a successful FRESCA mask fit.

The intent-to-treat (ITT) population will include all subjects who are considered enrolled and randomized. The ITT population will be used to determine any adverse event outcomes and assess study safety outcomes.

The modified intent-to-treat (mITT) population will include all intent-to-treat subjects who complete a valid PSG Study during randomized sleep nights 1 and 2. The mITT population will be used to assess study effectiveness outcomes.

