8. GENERAL STATISTICAL CONSIDERATIONS

All analyses will be pooled across the enrolling sites, except otherwise stated, and conducted using SASv9.4 or higher. All baseline summary tables will include each sequence group and all subjects combined, while all effectiveness and safety table will include each treatment group. All listings will include all subjects in the ITT population.

Descriptive statistics will be used to summarize all endpoints. For continuous variables the descriptive statistics will include the number of subjects, mean, standard deviation, median, and range. The descriptive statistics for categorical variables will include the number of subjects and percent (%).

Formatting of numerical results will include the following:

- Mean values will be reported to 1 additional decimal place than collected.
- Standard deviation values will be reported to 2 additional decimal places than collected.
- Median and range values will be reported as the data are collected.
- Percentages will be reported to 1 decimal place.
- Confidence intervals will be reported to the same number of decimal places as the mean values.
- P-values being reported to 3 decimal places.

In-text tables will be brought in from post-text tables for the clinical study report.

注臘SIMULSTAT

FRESCA Medical Protocol: 18-01 Statistical Analysis Plan v1.0 (17JUN2019)

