11. SAFETY ANALYSES

11.1 Adverse Events

Adverse events will be summarized descriptively by treatment group, system organ class, and preferred term. An additional summary will be provided for device and procedure related adverse events by treatment group, system organ class, preferred term and severity. Any SAEs or UADEs will be individually reported. A listing of all adverse events will be generated.

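### Adverse events in subjects who fail the pre-enrolment fit test on the investigational device reach no planned table or listing, and events before Night 1 have no defined reporting category

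*Protocol*

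**What the plan says.** **Exposure before enrolment.** The titration night uses neither study device: "This PSG titration study will be performed using a commercially-available CPAP mask and hose" (Protocol 10.3). After a valid titration night "and identification of a therapeutic pressure setting, the subject will be assessed for proper fit to the FRESCA mask", and the test is done on the new device: "The subject will breathe on the investigational device set to the titrated pressure for at least a 30-second interval". SAP 4.1 describes the same step on the investigational flow generator and mask.

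**Enrolment.** Being able to wear the FRESCA mask properly is inclusion criterion 4 (Protocol 9.2.1). Protocol 10.4 makes it a condition of enrolment: a subject must, among other things, "have a successful FRESCA mask fit. Each enrolled subject will be randomized to one of two sleep night sequences". Protocol 11.2 and SAP 4.2 repeat the condition.

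**Safety set.** Protocol 11.2 states: "The ITT population will be used to determine any adverse event outcomes and assess study safety outcomes". SAP 8 states: "All listings will include all subjects in the ITT population". SAP 13 and 14 give ITT as the population for Tables 14.3.1 and 14.3.2 and for the adverse event listings 16.3.9.1 and 16.3.9.2.

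**Collection and summary.** Table 1 in both documents marks adverse events from the titration night onward, and Protocol 10.6 includes an adverse event assessment among the titration-night data. The summary rule in SAP 11.1 is: "Adverse events will be summarized descriptively by treatment group, system organ class, and preferred term". Protocol 11.4.4 has the same rule, and both sections end by promising a listing of all adverse events.

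**The concern.** The fit test is a subject's first contact with the investigational device, and it comes before the point at which the safety set begins. Protocol 14.1 names claustrophobia, a panicky feeling and difficulty breathing as possible events. If one of these occurs at the fit test and the subject is not enrolled, the event belongs on the case report form but has no route into the report. The results are meant to support a 510(k) submission, where a reader would expect the listing to cover everyone who used the device.

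There is a second, lesser gap. An enrolled subject's event on the titration night, such as irritation from a PSG sensor or a facial mark from the mask, arises before either study device has been used for a night. The summaries have only device groups to hold it, and no rule says where it goes.

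**Working it through.** The plan gives no figure on this point, and its power calculation does not enter. The check is mainly a trace of the rules.

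**1. Who is fit-tested.** Under Protocol 10.3, subjects with a valid titration night and an identified pressure. Candidates who fail earlier never touch the investigational device.

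**2. Where a fit failure goes.** Criterion 4 is unmet, so the subject is a screen failure (Protocol 3) and is not enrolled (Protocol 10.4). The two ITT definitions differ slightly: enrolled and randomized in Protocol 11.2, enrolled in SAP 7. Both exclude this subject. Protocol 10.6 words the order of enrolment and randomization differently and does not mention fit separately, but it still requires the inclusion criteria, so the result is the same.

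**3. What is reported.** Read alone, SAP 8 could mean that listings contain at least the ITT subjects. SAP 14 removes that reading for adverse events by naming ITT as the population of 16.3.9.1 and 16.3.9.2. SAP 9.1 limits disposition to ITT and mITT, and the screening log in Protocol 10.4 records only whether a subject was enrolled. So the number fit-tested, and the number who failed, is not reported either.

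| Onset of event | Device used | Enrolled subject | Fit failure |
|---|---|---|---|
| Titration night | Commercial CPAP interface | Listed; summary group undefined | No planned output |
| Fit test | Investigational | Listed; summary group undefined | No planned output |
| Night 1, and the interval to Night 2 | First device in sequence | Listed; no written onset rule | Not applicable |
| Night 2 to exit | Second device in sequence | Listed; no written onset rule | Not applicable |

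**4. Possible number of people.** The documents give no fit-failure rate f, so the rates below are assumptions. With 50 enrolled, the number tested is 50/(1 − f) and the number failed is 50/(1 − f) − 50.

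- f = 2%: 51.0 tested, 1.0 failed
- f = 5%: 52.6 tested, 2.6 failed
- f = 10%: 55.6 tested, 5.6 failed
- f = 20%: 62.5 tested, 12.5 failed

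This counts people, not events. No event rate at the fit test is given, so no number of missing events can be derived.

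**5. Length of exposure.** The minimum of 30 seconds, set against the 4 hours of sleep needed for a valid night, is 30/(4 × 3,600) = 30/14,400 = 0.21%.

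**The case against.** The strongest reply is that little safety information is at risk. Protocol 14.1 requires adverse events to be recorded whatever their cause. Serious events must reach the sponsor or the EDC within 24 hours, and unanticipated device effects are reported onward (Protocol 14.5); neither duty is limited to ITT. The exposure may last only half a minute. Analysing safety in randomized subjects after a screening step is a common choice, and the step is described as a check of fit, not of tolerance.

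Most of this stands, and it limits the point to non-serious events in a few briefly exposed people. It does not close the gap. Non-serious events are the likely kind: Protocol 7.2 reports that most device events in the earlier study were asymptomatic or mild and that none were serious. And a listing promised for all adverse events should hold all of them.

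A reader might also infer that titration-night events will be charged to the wrong device. The documents do not show that. They are silent on attribution. Enrolled subjects' events still appear in the listing, the investigator judges the relationship to device and procedure for each event, and procedure-related events have their own table. Protocol 11.1 also asks for a column of all subjects combined, although SAP 8 gives safety tables by treatment group only. The gap is a missing rule, not a demonstrated error.

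**Conclusion.** The point holds in limited form. The stated rules exclude an exposed subject's non-serious event from every planned output, which conflicts with the promised listing of all adverse events. The handling of events before Night 1 is unspecified and could be settled by an analyst, but it should be written down before database lock.

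The effect is probably small and cannot be sized from the documents. The range of about 1 to 13 people rests on assumed failure rates of 2% to 20% and on full enrolment of 50. The primary AHI analysis is not affected.

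Three stronger readings are not supported. Not every candidate is exposed, only those who reach the fit test. The documents do not show that fit failures are the people least able to tolerate the device, since no tolerance criterion is set. And a comparison of event rates with and without fit failures would need event counts that the plan does not give, and would pool an exposure of perhaps 30 seconds with whole nights.

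**What to change.** Amend Protocol 11.2 and 11.4.4 and SAP 7, 8, 9.1 and 11.1 as follows.

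1. Extend listings 16.3.9.1 and 16.3.9.2 to every subject who breathed on the investigational device, whether or not randomized.
2. Add the numbers fit-tested and failed to the disposition summary.
3. Show events with onset before the start of Night 1 in a separate pre-randomization category, marked as titration night or fit test. Define the category by the start of Night 1, because the SAP's Table 1 footnote allows randomization as soon as the titration night has succeeded and the subject is enrolled.
4. Assign each later event to the device most recently used at onset: the first device from the start of Night 1 until the start of Night 2, and the second from the start of Night 2 to study exit. A rule that counted any event starting on or after a device's night would place Night 2 events under both devices.

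No study procedure changes. The cost is one extra category, a wider listing and a fit-result field if none exists; the titration data items in Protocol 10.6 show none. The sponsor should also confirm that case report forms are kept for fit failures, because Protocol 20.6 speaks of recording data for enrolled subjects. The reported count of investigational-device events may rise slightly.

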10.4 Randomization

Each site will be provided a list of subject numbers to be assigned to subjects as they are evaluated at their screening visit. A screening log will record the subject number, subject initials, date of screening, date informed consent was signed, and whether subject was enrolled. A subject is considered enrolled if they sign the informed consent document, meet all inclusion and exclusion criteria, complete a valid PSG titration study that identifies a therapeutic pressure setting (i.e., AHI < 10/hr.) and have a successful FRESCA mask fit. Each enrolled subject will be randomized to one of two sleep night sequences. Randomization assignments will be computer-generated by the study statistician and obtained through the data management system (EDC). A randomization log will be used to record the assigned randomization sequence.

10.5 Baseline Evaluation

- 1) Baseline information:
 - a) Patient identifier
 - b) Date of birth
 - c) Gender
 - d) Ethnicity
 - e) Height (inches)
 - f) Weight (pounds)
 - g) BMI (calculated from height and weight)
- 2) Physical Examination:
 - a) Vital signs (HR, BP, Oral temperature)
- 3) Medical history, including but not limited to:
 - a) Cardiovascular disease
 - b) Cancer
 - c) Respiratory disease
 - d) Psychiatric illness
 - e) Prior surgical intervention for OSA
 - f) Non-OSA sleep disorders

¹ Current CPAP users cannot use the same brand and model CPAP mask as they currently use at home.

- g) Severe nasal allergies, sinusitis or nasal blockages
- 4) Listing and dosages of all current prescription medications or other agents that may affect sleep and/or PSG results

10.6 **Detailed Description of Study Procedures**

This study is not blinded, as both the investigator and subject will be aware of the therapy that is being utilized. However, investigators and study staff will minimize discussion about the particular therapy. Since the outcome measures are objective observations of each subject's sleep architecture and respiratory events, and the scoring of the PSGs will be performed by a masked central scorer, bias resulting from the open label nature of this study will be minimized.

Consented subjects who met the inclusion / exclusion criteria and completed a valid PSG titration study will be randomized. Following randomization, subjects are considered enrolled.

Subjects will undergo one in-lab PSG titration study to identify their therapeutic pressure setting. Subjects who complete a valid PSG titration study will be scheduled for two additional sleep nights, preferably two consecutive nights. The number of allowable calendar days between the two randomized sleep nights is 0 - 10 days. These sleep nights will be randomized to one of two sequences.

Sequence 1: Original (predicate) FRESCA device set to PSG-titrated fixed pressure on night 1 / investigational FRESCA Airbox device set to auto-adjusting pressure + EPR on night 2.

Sequence 2: Investigational FRESCA Airbox device set to auto-adjusting pressure + EPR on night 1 / Original (predicate) FRESCA device set to PSG-titrated fixed pressure on night 2.

If the subject fails to have a valid PSG Study on either night, the subject is considered an early study exit and excluded from the mITT analysis of the primary effectiveness endpoint. These subjects will be analyzed and summarized separately, including the reason(s) they did not complete a valid PSG study.

The following data will be collected for the PSG titration study night and PSG randomized sleep nights 1 and 2:

PSG Titration Study

- 1) Date of PSG Titration
- 2) Brand and model of PSG equipment
- 3) Mask style used during titration
- 4) Brand and model of CPAP flow generator
- 5) Brand and model of CPAP mask used²
- 6) Total test time (min)
- 7) Total sleep time (min)

² Current CPAP users cannot use the same brand and model CPAP mask as they currently use at home.

- 8) AHI (overall)/h
 9) ODI (overall)/h
 10) Sleep efficiency %
 11) Arousal index ((overall)/h
 12) Minimum sleep SpO₂ %
 13) Mean sleep SpO₂ %
 14) Wakefulness (min)
 15) Stage N1 (min)
 16) Stage N2 (min)
 17) Stage N3 (min)
 18) REM (min)
 19) Prescribed pressure setting (cmH₂O)
- 20) Adverse event assessment

PSG Sleep Nights 1 and 2

- 1) Date of sleep night
- 2) Brand and model of PSG equipment
- 3) FRESCA mask type (nasal pillow or nasal mask)
- 4) Device type (predicate or investigational)
- 5) Device mode (PAP, Auto-adjusting pressure)
- 6) Fixed pressure (if PAP mode)
- 7) Auto-adjusting pressure range (if auto-adjusting pressure mode)
- 8) EPR setting
- 9) Lights off (24-hr. clock)
- 10) Lights on (24-hr. clock)
- 11) Duration of sleep ≥ 4 hrs (Yes or No)
- 12) Sleep night notes (i.e., in-room adjustments, equipment technical issues)
- 13) Medication changes since prior PSG night
- 14) Adverse event assessment

PSG Central Scoring of Sleep Nights 1 and 2

- 1) Date EDF File was Scored
- 2) Date of Sleep Night
- 3) Sleep Night Number
- 4) Total test time (min)
- 5) Total sleep time (min)
- 6) AHI (overall)/h
- 7) ODI (overall)/h
- 8) Sleep efficiency %
- 9) Arousal index ((overall)/h
- 10) Minimum sleep SpO₂ %
- 11) Mean sleep SpO₂ %
- 12) Wakefulness (min)
- 13) Stage N1 (min)
- 14) Stage N2 (min)

15) Stage N3 (min)16) REM (min)17) Comments/notes

10.7 Study Withdrawal Criteria

An enrolled subject will be exited from the study when any of the following occurs:

- 1. Subject withdraws consent.
- 2. The investigator removes them from the study for their welfare.
- 3. Subject is non-compliant with study procedures.
- 4. Subject fails to return for a study visit and does not respond to 3 documented contact attempts.

11 STATISTICAL CONSIDERATIONS

11.1 General Considerations

All data collected will be listed and summarized descriptively. All analyses will be pooled across the enrolling sites, unless otherwise specified, and conducted using SAS v9.4 or higher. All summary tables will include each treatment group and all subjects combined.

Descriptive statistics for categorical variables will be summarized with frequencies and percentages, while continuous variables will be summarized with n, mean, median, standard deviation, and range.

Further details will be provided in the Statistical Analysis Plan.

11.2 Analysis Populations

The enrolled population will include all subjects who sign the informed consent document, meet all inclusion and exclusion criteria, complete a valid PSG titration study that identifies a therapeutic pressure setting (i.e., AHI < 10/hr). and have a successful FRESCA mask fit.

The intent-to-treat (ITT) population will include all subjects who are considered enrolled and randomized. The ITT population will be used to determine any adverse event outcomes and assess study safety outcomes.

The modified intent-to-treat (mITT) population will include all intent-to-treat subjects who complete a valid PSG Study during randomized sleep nights 1 and 2. The mITT population will be used to assess study effectiveness outcomes.

11.3 Sample Size

A sample size calculation was performed for the primary analysis of demonstrating noninferiority of FRESCA Airbox treatment against the predicate (control) FRESCA treatment. It is planned to enroll up to 50 subjects across up to 6 study sites to yield at least 38 evaluable (mITT) subjects. Using 38 evaluable subjects for the primary analysis will provide 85% power to demonstrate non-inferiority assuming the mean difference between treatments is 0. These calculations also assume a 1-sided alpha level of 0.025%, standard deviation of 5 units, and a NI margin of 5 units. Sample size calculations were performed using the POWER procedure in SASv9.4, assuming a 2-group t-test between treatments, assuming a period effect in the ANOVA model as described in Section 11.4.

11.4 Statistical Analyses

11.4.1 Primary Endpoint Analysis

The primary endpoint in this study is mean AHI values. It is hypothesized that the new device treatment will be non-inferior to the predicate device treatment in mean AHI. The following 1-sided hypothesis will be tested for AHI:

H0: μ NEW - μ PREDICATE $\geq 0 + \Delta$

versus

HA: μ NEW - μ PREDICATE < 0 + Δ

Where μ NEW represents the mean AHI for the new device treatment, μ PREDICATE represents the mean AHI for the predicate device treatment, and Δ represents the non-inferiority margin. This analysis will assume a non-inferiority (NI) margin of 5 units and a 1-sided alpha level of 2.5%. A 2-sided 95% confidence interval (CI) will also be provided around the difference between treatments, where non-inferiority will also be demonstrated if the upper bound of the 95% CI is less than or equal to the NI margin of 5 units. In this scenario the 2-sided 95% CI equates to testing the 1-sided non-inferiority hypothesis.

The hypothesis will be tested using a t-test between treatments from an analysis of variance (ANOVA) model with treatment, sequence, and period as fixed effects and subject as a random effect. This model assumes no carry over effect.

The population for this primary endpoint analysis is the mITT population. The mITT population, by definition, will not have any missing data and hence, there will not be any imputation methods applied.

